10.3 Required prophylaxis

The following prophylactic measures are required:

- Tafasitamab infusion-related reaction (IRR) prophylaxis (per the [MSK tafasitamab infusion guideline](#))
- Lenalidomide-associated venous thromboembolism (VTE) prophylaxis: Patients must receive VTE prophylaxis throughout the induction phase
- HBV reactivation prophylaxis: in patients positive for HBcAb and/or HBsAg without detectable viral load, prophylaxis against reactivation (eg, entecavir 0.5mg PO daily; consult pharmacist for dosing in patients with renal dysfunction) should be administered throughout study treatment and 6 months after EOT
- Tumor lysis syndrome (TLS) prophylaxis:
 - Patients must be screened for risk of TLS prior to study treatment initiation according to the [MSK guideline for prevention and management of TLS in adults](#)
 - Patients at risk of TLS should undergo risk-adapted prophylaxis and monitoring according to the [institutional guideline](#) and investigator's discretion

10.4 Study duration

The maximum duration of treatment for this study is planned to be a total of 36 cycles (12 cycles of tafasitamab plus lenalidomide induction, 24 cycles of tafasitamab maintenance), not to exceed 36 months.

After discontinuation of both study drugs, patients will complete an EOT visit within 7 days from the date of official treatment discontinuation. If treatment must be discontinued due to prolonged interruption for toxicity (see 10.5.7), the EOT visit will occur within 7 days of the decision to permanently discontinue treatment.

All patients will be followed for adverse events for at least 30 days following the last dose of study treatment or until initiation of new therapy, whichever comes first. Patients who proceed to tafasitamab maintenance will be followed for disease status updates for up to three years. After completing study treatment, survival, relapse, and new anti-lymphoma therapy information will be collected via telephone calls, patient medical records, and/or clinic visits approximately every 6 months until death, loss to follow up or consent withdrawal, whichever comes first.

10.5 Dose continuation, modification, and interruption

Patients will be evaluated for AEs at each visit and will undergo laboratory evaluations according to the schedule in Section 11.0 and Table 11-1. CTCAE version 5.0 will be utilized for toxicity grading.

The course of action for treatment interruption, modification, and/or reinstatement for specific toxicities is outlined below. Any other treatment interruption considered medically necessary by the investigator is permitted, and the decision and rationale should be documented.

10.5.1 Parameters for treatment continuation

Patients may initiate treatment on day 1 of each cycle provided that:

- ANC 1,000 cells/mcl (unless felt to be secondary to underlying MCL)
- Platelets 50,000 cells/mcl (unless felt to be secondary to underlying MCL)
- No serious organ or other toxicity present

10.5.2 Tafasitamab infusion-related reactions

10.5.2.1 Monitoring, grading, and acute management of tafasitamab IRR

Vital signs will be monitored during tafasitamab infusion as outlined in Section 11.0, Table 11-1. Body temperature, systolic and diastolic blood pressure (mmHg), heart rate (beats per minute), and respiratory rate (respirations per minute) will be measured immediately prior to infusion, at 15 ± 5 and 30 ± 10 minutes after initiating infusion, every 60 ± 15 minutes

thereafter, and at the end (\pm 20 minutes) of infusion. If the infusion is interrupted and/or subsequently restarted, vital signs should be assessed every 60 ± 15 minutes after the first hour. Vital signs may be monitored more frequently if clinically indicated.

All patients will receive IRR prophylaxis for at least the first 3 doses of tafasitamab as described in Section 10.3. IRRs will be assessed according to CTCAE version 5.0 grading:

Table 10-2: Tafasitamab infusion-related reaction grading

Grade 1	Grade 2	Grade 3	Grade 4
Mild, transient reaction; infusion interruption not indicated; intervention not indicated	Therapy or infusion interruption indicated but respond promptly to symptomatic treatment (eg, antihistamines, NSAIDs, narcotics, IV fluids); prophylactic medications indicated for ≥ 24 hours	Prolonged (eg, not rapidly responsive to symptomatic medication and/or brief interruption of infusion); recurrence of symptoms following initial improvement; hospitalization indicated for clinical sequelae	Life-threatening consequences; urgent intervention indicated

Precautions for anaphylaxis will be observed during tafasitamab infusion. Emergency resuscitation equipment and medications will be readily available, including medications in the Hypersensitivity Order Set (Chemo_Adult_Hypersensitivity_Order_Set (Outpatient)). Acute management of signs and symptoms of IRR will be according to the [MSK institutional standard](#) (Appendix C).

10.5.2.2 Rechallenge after tafasitamab IRR

For grade 2 and 3 IRRs, once symptoms have resolved to grade ≤ 1 according to investigator assessment, the infusion may be resumed according to the [MSK tafasitamab infusion guideline](#).

For grade 4 IRRs, the patient must not receive further treatment with tafasitamab. Treatment with lenalidomide alone may continue.

10.5.3 Lenalidomide-associated diarrhea

Diarrhea suspected to be secondary to lenalidomide will be graded according to CTCAE version 5.0. Interruptions of lenalidomide and dose reductions will be based on grade:

Table 10-3: Lenalidomide-associated diarrhea grading and dose interruption/reduction

Grade 1-2	Increase of ::;; 4-6 stools per day over baseline; mild-moderate increase in ostomy output compared to baseline; limiting instrumental activities of daily living (AOL)	No interruption or dose reduction required Implement supportive care measures; see suggested symptom management measures (Appendix D)
Grade 3-4	Increase of 7 stools per day over baseline; hospitalization indicated; severe increase in ostomy output compared to baseline; limiting self care AOL; life-threatening consequences; urgent intervention indicated	Interrupt lenalidomide dosing Implement supportive care measures; see suggested symptom management measures (Appendix D)
	Resolution to grade ::;; 2	Resume lenalidomide dosing at the next lower dose level (Table 10-6)

10.5.4 Hematologic and other toxicities

Toxicities suspected to be related to study medications will be graded according to CTCAE version 5.0 and managed according to Tables 10-4 and 10-5 below.

Table 10-4: Hematologic and other toxicities suspected to be related to either study medication

Thrombocytopenia grade 3-4	Platelets < 50,000 cells/mcL	Cycles 1 through 3: interrupt both tafasitamab and lenalidomide Cycle 4: interrupt lenalidomide only Obtain CBC every 7 days
	Platelets recover to 50,000 cells/mcL	Provided other criteria for dosing are met (see 10.5.1), resume study treatment. If lenalidomide is being continued, it should be resumed at the next lower dose level. Dose re-escalation is permitted in certain circumstances (Table 10-6).

Neutropenia grade 3-4	ANC < 1,000 (but 500) cells/mcl for 7 days Or ANC < 1,000 cells/mcl with fever 38.5°C (101°F) Or ANC < 500 cells/mcl	Cycles 1 through 3: interrupt both tafasitamab and lenalidomide Cycle 4: interrupt lenalidomide only Obtain CBC every 7 days GCSF use is strongly encouraged
	ANC recovers to 1,000 cells/mcl	Provided other criteria for dosing are met (see 10.5.1), resume lenalidomide. If lenalidomide is being continued, it should be resumed at the next lower dose level. Dose re-escalation is permitted in certain circumstances (Table 10-6).
Other clinically significant toxicities (except those attributable to lenalidomide below)	Grade 3-4	Interrupt the study drug(s) to which the toxicity is suspected to be attributable.
	Resolution to grade :s; 2	Provided other criteria for dosing are met (see 10.5.1), resume previous treatment. If lenalidomide was interrupted and is being continued, it should be resumed at the next lower dose level (Table 10-6)

Table 10-5: Other toxicities suspected to be related to lenalidomide

Thromboembolic events	Grade 3-4	Interrupt lenalidomide dosing Start anticoagulation as per MSK anticoagulation guideline and investigator's discretion
	Resolution to grade :s; 2	Resume lenalidomide at investigator's discretion (maintain dose level)

Allergic reaction or hypersensitivity grade 3-4 (including but not limited to Stevens-Johnson syndrome, toxic epidermal necrolysis, exfoliative or bullous rash, angioedema)	Discontinue lenalidomide permanently
Desquamating (blistering) rash grade 3-4	Discontinue lenalidomide permanently
Nondesquamating rash	Grade 1 (< 10% of body surface area (BSA)) Treat with topical corticosteroids and oral antihistamines until resolution of rash/symptoms; short course of low-dose oral corticosteroid is permitted
	Grade 2 (10-30% of BSA) Consider interrupting lenalidomide dosing until grade :5 1 Treat with topical corticosteroids and oral antihistamines until resolution of rash/symptoms to grade s; 1; short course of low-dose oral corticosteroid is permitted
	Grade 3 (> 30% of BSA) Interrupt lenalidomide dosing until grade s; Treat with topical corticosteroids and oral antihistamines until resolution of rash/symptoms to grade :5 1; short course of low-dose oral corticosteroid is permitted
	Grade 4 (life-threatening) Discontinue lenalidomide permanently
Tumor flare reaction grade 1-2	Continue lenalidomide at current dose level or interrupt lenalidomide at investigator's discretion

Tumor flare reaction grade 3-4	Grade 3-4 (see 10.5.5)	Interrupt lenalidomide dosing
	Resolution to grade 1	Resume lenalidomide (maintain dose level)

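### Table 10-4's neutropenia row holds both drugs in cycles 1 to 3, but its recovery cell restarts only lenalidomide

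*Combined protocol and SAP*

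**What the plan says.** Table 10-4 in section 10.5.4 pairs an interruption rule with a recovery rule for three kinds of toxicity.

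The neutropenia row has three triggers: a lower-grade band that must persist ("ANC < 1,000 (but 500) cells/mcl for 7 days"), ANC below 1,000 with fever, and ANC below 500. Its action cell begins "Cycles 1 through 3: interrupt both tafasitamab" and goes on to name lenalidomide as well. From cycle 4, only lenalidomide is held. During the hold the row asks for "Obtain CBC every 7 days GCSF use is strongly encouraged". Its recovery condition is "ANC recovers to 1,000 cells/mcl", and the instruction beside it is "Provided other criteria for dosing are met (see 10.5.1), resume lenalidomide". The next sentence says that lenalidomide, if it is continued, restarts one dose level lower.

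The thrombocytopenia row has the same hold rule, but its recovery instruction is "Provided other criteria for dosing are met (see 10.5.1), resume study treatment". The row for other clinically significant toxicities holds whichever drug is suspected, and its instruction is "Provided other criteria for dosing are met (see 10.5.1), resume previous treatment".

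Some comparison signs were lost when the text was read from PDF. I take the missing signs as 'at least' in the ANC levels, the 7 days and the cycle 4 rule, and as 'up to' in the first sentence of 10.5.7. Neither those losses nor any redaction explains the difference in wording between the recovery cells.

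**The concern.** This is an operative dosing rule. In cycles 1 to 3 the row stops two drugs and then tells staff to restart one. Tafasitamab has no restart instruction of its own in the middle of a cycle, which is when most of its early infusions fall due: section 10.1 schedules it on days 1, 8, 15 and 22 of each of these cycles, plus day 4 of cycle 1. Followed to the letter, the cell would have staff withhold an infusion from a patient whose count has already recovered. What is at stake is avoidable missed tafasitamab doses and inconsistent handling of patients in the same situation.

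**Working it through.** The plan gives no figure to reproduce. The check compares the cells, then looks for a rule elsewhere that fills the gap.

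**Step 1: does each row restart what it stops?**

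| Row of Table 10-4 | Held in cycles 1 to 3 | Restarted on recovery | All held drugs covered? |
|---|---|---|---|
| Thrombocytopenia | Both drugs | Study treatment | Yes |
| Neutropenia | Both drugs | Lenalidomide | No, tafasitamab omitted |
| Other toxicities | The suspected drug or drugs | Previous treatment | Yes |

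**Step 2: is the omission likely to be deliberate?** Two things suggest not. First, the follow-on sentence about lenalidomide being continued is the same in the neutropenia and thrombocytopenia rows. It makes sense after an instruction covering both drugs and is awkward after one that has just restarted lenalidomide. Second, where the protocol means to end tafasitamab it says so, as in section 10.5.2.2: "For grade 4 IRRs, the patient must not receive further treatment with tafasitamab". The neutropenia cell does not forbid tafasitamab; it is silent on it.

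**Step 3: do the general rules fill the gap?** Section 10.5.1 allows treatment to start on day 1 of a cycle once ANC is at least 1,000 and the other criteria are met, without naming a drug. It does not cover days 8, 15 or 22. Section 10.5.7 has treatment continue at the next scheduled visit after an interruption of up to 28 days, without tying that to ANC recovery or to either drug. A reader can infer a restart from these rules, but neither is a mid-cycle recovery instruction for tafasitamab after neutropenia.

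**Step 4: how much could be withheld?** With 28-day cycles, the next day 1 is day 29, so the time to it is 29 minus the day the hold starts. Assume that the ANC has recovered by the next weekly infusion day and that tafasitamab then waits for day 1. Cycle 1 day 1 is left out because no study drug has yet been given.

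| Hold starts on | Days to next day 1 | Infusions that could be withheld after recovery |
|---|---|---|
| Day 1 (cycles 2, 3) | 29 − 1 = 28 | Days 8, 15, 22 (three) |
| Day 4 (cycle 1) | 29 − 4 = 25 | Days 8, 15, 22 (three) |
| Day 8 | 29 − 8 = 21 | Days 15, 22 (two) |
| Day 15 | 29 − 15 = 14 | Day 22 (one) |
| Day 22 | 29 − 22 = 7 | None |

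Cycles 1 to 3 contain 5 + 4 + 4 = 13 scheduled infusions, so one hold puts at most three of 13 in doubt.

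**Example with assumed counts.** ANC is 400 on cycle 2 day 8, and both drugs are held. ANC is 1,000 on day 15. Lenalidomide restarts one level lower. Tafasitamab on days 15 and 22 is given if staff apply 10.5.7, or withheld until cycle 3 day 1 if they follow the cell literally.

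**The case against.** The strongest reply is that the meaning can be recovered. The adjacent row has the same hold and the inclusive wording, 10.5.1 and 10.5.7 both point toward restarting, and this is a single-center study run by one lymphoma service. That is fair and keeps the point small. It does not remove it, because staff must still set aside the cell written for this toxicity to reach the intended answer.

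Four stronger readings are tempting, and the documents do not support them.

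- **Permanent discontinuation.** A reader might infer that tafasitamab stays on hold past 28 days and is then lost under 10.5.7. As step 4 shows, no hold starting on a cycle 1 to 3 infusion day is more than 28 days from the next day 1. If counts qualify then, 10.5.1 allows treatment. From cycle 4 the row no longer holds tafasitamab at all. The outcome is remote. It is not impossible: counts may still be low on that day 1, and a hold starting on a day 1 sits exactly at the limit on nominal visit days.
- **Tafasitamab restarted below ANC 1,000.** A reader might argue that 10.5.7 lets tafasitamab restart at, say, an afebrile ANC of 700 on day 15 after 400 on day 8. That places a general sentence above the row's own recovery level, which names no drug. It also needs the 7-day clock to start afresh when the count moves from 400 to 700. And an afebrile 700 lasting under 7 days would not by itself interrupt either drug mid-cycle. The reading is strained.
- **Many patients affected.** Table 15-1 gives grade 3-4 neutropenia in 49% of 81 patients. That study was in another lymphoma and used lenalidomide 25mg rather than 20mg, and its figure is not limited to cycles 1 to 3 or to these triggers. It is not an estimate for this trial.
- **Damage to the primary analysis.** Nothing in the documents links a few withheld infusions to a change in ORR or in the Simon design's type I error or power.

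**Conclusion.** The neutropenia recovery cell is wrong as written: it is the only one of Table 10-4's three recovery cells that does not cover every drug its row stops. The severity is minor. The practical effect is confined to cycles 1 to 3 and to mid-cycle infusions after the ANC has recovered. It amounts to at most three infusions per hold, and none if staff read the cell as it was probably meant. The size rests on nominal visit days, on recovery by the next weekly infusion day, and on the missing comparison signs being as I have taken them. The mismatch between cells depends on none of these. The documents give no basis for estimating how many patients would be affected.

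**What to change.** In the neutropenia recovery cell of Table 10-4, replace *resume lenalidomide* with *resume study treatment*, as in the thrombocytopenia row, and keep the sentences that follow. Both held drugs then restart once ANC reaches 1,000 and the other dosing criteria are met, with lenalidomide at the next lower dose level. From cycle 4 nothing changes, because only lenalidomide is held. The cost is one phrase in the next amendment. No threshold, dose level, sample size or analysis is altered.

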10.5.5 Lenalidomide-associated tumor flare

Patients should be monitored at each visit for tumor flare reactions (TFRs). TFR is defined as a sudden and tender increase in the size of the disease bearing sites (such as lymph nodes, spleen, and/or liver), often accompanied by low-grade fever, non-pruritic diffuse rash, and in some cases, an increase in peripheral blood lymphocyte count. Such reactions are expected with lenalidomide, especially in patients with a high burden of disease and may mimic disease progression. Therefore, careful monitoring and evaluation is important prior to discontinuing a study patient for progressive disease in the initial cycles of lenalidomide therapy. There are currently no laboratory or radiological tests to help distinguish TFR from POD. The distinction should be made on clinical grounds, incorporating observations such as associated physical findings, laboratory findings, and pace of disease before and after study treatment initiation. TFR should be recorded as an AE of special interest, graded using CTCAE version 5.0, and not as POD.

Treatment of TFR is at the discretion of the investigator.

10.5.6 Lenalidomide dose reductions for toxicity

If lenalidomide dosing was interrupted during the previous cycle, restarted at the next lower dose level during the same cycle in which it was interrupted, and did not require interruption for the remainder of the cycle, then that reduced dose level will be initiated on day 1 of the next cycle. There will be no more than one dose reduction from one cycle to the next.

A dose reduction of lenalidomide constitutes a 5mg decrease in the daily dose from the previous dose, including in patients who initiate treatment at a decreased dose due to renal dysfunction. Patients who are unable to tolerate the lowest dose of 5mg once daily should discontinue lenalidomide but continue treatment with tafasitamab alone.

Table 10-6: Lenalidomide dose reductions for toxicity		Note
Starting dose	20mg once daily days 1-21 of each 28-day cycle	In patients who required lenalidomide dose reduction for hematologic toxicity early in the treatment course due, in the opinion of the investigator, to bone marrow and/or splenic disease
Dose level -1	15mg once daily days 1-21 of each 28-day cycle	
Dose level -2	10mg once daily days 1-21 of each 28-day cycle	

Dose level -3	5mg once daily days 1-21 of each 28-day cycle	involvement, re-escalation to the previous dose level is permitted
Further reduction indicated	Discontinue	

10.5.7 Maximum duration of treatment interruption

If treatment is interrupted for 28 consecutive days, treatment should continue at the next protocol scheduled visit. No missed visits or doses of either drug should be made up.

If treatment with one study drug is interrupted for more than 28 consecutive days, that drug is to be permanently discontinued and the patient will continue treatment with the other study drug per protocol. If treatment with both study drugs is interrupted for more than 28 consecutive days, the EOT visit will be performed as noted in 10.4.

11.0 EVALUATION DURING TREATMENT/INTERVENTION

11.1 General overview of evaluations

Evaluations during screening and study treatment are as indicated in Table 11-1.

Table 11-1. Schedule of evaluations (screening through cycle 3).

Day	Screening		Cycle 1 (28 days)					Cycle 2 (28 days)					Cycle 3 (28 days)				
	S 28 days before C1D1	S 7 days before C1D1	1	4	8	15	22	1	8	15	22	1	8	15	22	1	8
Window					±1	±1	±1	±1	±1	±1	±1	±1	±1	±1	±1	±1	±1
Informed consent	X																
Inclusion/exclusion checklist	X			X6													
Biopsy and pathologic confirmation of MCL	X																
PET	X															X	
CT CAP (+neck if indicated)	X															X	
KPS	X		X					X				X				X	
Vital signs ¹	X		X	X	X	X	X	X	X	X	X	X	X	X	X	X	X
Height			X														
Weight			X					X				X			X		
CBC with differential		X	X		X	X	X	X	X	X	X	X	X	X	X	X	X
Chemistry ²		X	X					X				X			X		
Hepatitis B serology	X																
Hepatitis C serology	X																
HIV serology	X																
Pregnancy test (if applicable) ³	X		X					X				X			X		
Consent to 12-245 IMPACT and sample collection ⁴	X																
BM aspirate and biopsy	X																
Research blood tests			X					X	X								
Optional research biopsy ⁵	X							X									
(S)AE assessment	X	X	X	X	X	X	X	X	X	X	X	X	X	X	X	X	X
Tafasitamab administration			X	X	X	X	X	X	X	X	X	X	X	X	X	X	X
Lenalidomide administration																	
Patients will self-administer Days 1-21 of each Cycle																	

Table 11-1 (continued). Schedule of evaluations (cycles 4 through EOT).

	Cycle 4 (28 days)	Cycle 5 (28 days)	Cycle 6 (28 days)	Cycle 7 (28 days)	Cycle 8 (28 days)	Cycle 9 (28 days)	Cycle 10 (28 days)	Cycle 11 (28 days)	Cycle 12 (28 days)	Cycle 13 (28 days)	Cycles 14-36 (28 days each)	EOT visit
Day	1	15	1	15	1	15	1	15	1	15	1	1
PET Scan												
CT CAP												
Biopsy												
KPS	X	X	X	X	X	X	X	X	X	X	X ⁸	X ⁹
Vital signs ¹	X	X	X	X	X	X	X	X	X	X	X	X ⁹
Weight	X	X	X	X	X	X	X	X	X	X	X	X ¹⁰
CBC with differential	X	X	X	X	X	X	X	X	X	X	X	X
Chemistry ²	X	X	X	X	X	X	X	X	X	X	X	
Pregnancy test (if applicable) ³	X	X	X	X	X	X	X	X	X	X	X	
BM aspirate and biopsy												
Research blood tests	X											
Optional research biopsy ⁵												
(S)AE assessment	X	X	X	X	X	X	X	X	X	X	X	X
Tafasitamab administration	X	X	X	X	X	X	X	X	X	X	X	X
Lenalidomide administration												

Patients will self-administer Days 1-21 of each Cycle

¹Vitals: Blood Pressure, Pulse, Respiratory Rate, and Temperature

²Chemistry: CMP, Phosphorus, Uric Acid, and LDH

³Patients able to become pregnant must have pregnancy testing performed according to Revlimid/lenalidomide REMS requirements: one test (sensitive to at least 50mIU/mL) 10-14 days before writing the initial lenalidomide prescription, and a second test within 24 hours prior to writing the initial lenalidomide prescription. Subsequent pregnancy testing should occur every 4 weeks.

⁴Unless previously performed within 6 months of study initiation

⁵Optional biopsy can be a fine needle aspirate or other biopsy of involved peripheral lymph node tissue, and/or bone marrow aspirate (if MCL involvement of marrow was demonstrated pre-treatment). Optional biopsy/aspirate occurs at baseline, cycle 1 between day 22-28, and at end of treatment/disease progression. Note that the biopsy performed for required confirmation of R/R MCL diagnosis is acceptable for the first research biopsy, provided that tissue is available, the biopsy was performed within the screening period, and the site can be re-biopsied at cycle 1 day 22.

⁶Prior to study drug administration

⁷Evaluation by CT CAP with IV contrast (include neck if disease involvement).

⁸Evaluation by PET/CT approximately every 6 months from previous scan

⁹Only required if not performed in the cycle before the EOT visit

¹⁰Only required for discontinuation for POD

